5.1.3 Anticipated regions and countries

The study will be conducted in North America, Europe, Japan, and China with possible extension to other regions or countries.

5.2 Schedule of study assessments

The schedule of assessments is presented in [Table 5-1](#).

This document cannot be used to support any marketing authorization application and any extensions or variations thereof.

REDACTED COPY

Table 5-1: Schedule of assessments

	Evaluation Period ^a									Taper Period (including 1 Wk drug free)	SFU (30 days after last PSL intake)				
	Entry Visit	Bi-weekly Visits		Monthly Visits		Visits every 3 M		EOS Visit	EDV Visit				End of Taper Visit	SFU Visit	Unsch Visit/TC
	V1 ^b	V2	V3	V4	V5	V6, V8, V10	V7, V9, V11	EOS ^c	EDV ^c						
Assessments	Wk 0	Wk 2	Wk 4	M2	M3	M6, M12, M18	M9, M15, M21	M24		Up to 4 Wk					
Written informed consent	X														
Dispensation of Subject Trial card	X														
Demographic data	X														
Verification of inclusion/exclusion criteria	X														
Verification of withdrawal criteria		X	X	X	X	X	X		X						
Medical history update	X														
C-SSRS since last visit ^d	X*	X	X	X	X	X	X	X	X	X	X				
HADS ^d	X			X		X	X	X	X						
SSG	X				X	X	X	X	X						
QOLIE-31-P ^d						X		X	X						
CIWA-B ^d								X ^c	X	X	X				
TSQM-9 ^d								X	X						

Table 5-1: Schedule of assessments

	Evaluation Period ^a									Taper Period (including 1 Wk drug free)	SFU (30 days after last PSL intake)				
	Entry Visit	Bi-weekly Visits		Monthly Visits		Visits every 3 M		EOS Visit	EDV Visit				End of Taper Visit	SFU Visit	Unsch Visit/TC
	V1 ^b	V2	V3	V4	V5	V6, V8, V10	V7, V9, V11	EOS ^c	EDV ^c						
Assessments	Wk 0	Wk 2	Wk 4	M2	M3	M6, M12, M18	M9, M15, M21	M24		Up to 4 Wk					
Vital signs ^f	X*	X	X	X	X	X	X	X	X	X	X				
Body weight	X*		X		X	X	X	X	X		X				
Physical examination ^g (XF = Full – XB = Brief)	XF*		XB		XB	XB	XB	XB	XB	XB	XB				
Neurological examination ^h (XF = Full – XB = Brief)	XF*		XB		XB	XB	XB	XB	XB	XB	XB				
Psychiatric and Mental Status	X*		X		X	X	X	X	X	X	X				
Personal Outcomes assessment ⁱ						X	X								
12-lead ECG ^j	X*		X		X		X	X	X		X				
Echocardiogram ^k		X			X	X	X	X ^k			X				
Blood/urine sample for clinical laboratory analysis	X*		X	X	X	X	X	X	X						
Pregnancy test (female subjects only) ^l	X*	X	X	X	X	X	X	X	X	X					

Table 5-1: Schedule of assessments

	Evaluation Period ^a									Taper Period (including 1 Wk drug free)	SFU (30 days after last PSL intake)	Unsch Visit/TC
	Entry Visit	Bi-weekly Visits		Monthly Visits		Visits every 3 M		EOS Visit	EDV Visit			
	V1 ^b	V2	V3	V4	V5	V6, V8, V10	V7, V9, V11	EOS ^c	EDV ^c			
Assessments	Wk 0	Wk 2	Wk 4	M2	M3	M6, M12, M18	M9, M15, M21	M24		Up to 4 Wk		
Seizure evaluation (count and type) ^m	X*	X	X	X	X	X	X	X	X	X	X	
Concomitant medications and procedures ⁿ	X*	X	X	X	X	X	X	X	X	X	X	
Recording of adverse events	X*	X	X	X	X	X	X	X	X	X	X	
Health-related outcomes and HRU	X*	X	X	X	X	X	X	X	X	X	X	
IRT call	X										X	
PSL dispensing (IRT)	X	X	X	X	X	X	X	X ^p	X			
PSL accountability and return ^o		X	X	X	X	X	X	X	X	X		
Study termination								X ^q			X ^r	

AED=antiepileptic drug; BP=blood pressure; CIWA-B=Clinical Institute Withdrawal Assessment-Benzodiazepines; C-SSRS=Columbia-Suicide Severity Rating Scale; ECG=electrocardiogram; EDV=Early discontinuation Visit; EOS=End of Study; HADS=Hospital Anxiety and Depression Scale; HRU=healthcare resource utilization; IRT=interactive response technology; M=month; PSL=padsevonil; QOLIE-31-P=Quality of Life Inventory in Epilepsy-31-P; SFU=Safety Follow-up; SSG=Seizure Severity Global Item; TC=telephone call; TSQM=Treatment Satisfaction Questionnaire for Medication; Unsch=unscheduled; V=visit; Wk=week

- ^a At any point during the Evaluation Period, an unscheduled visit may be conducted due to safety or efficacy reasons. Appropriate assessments will be conducted in relation to the reason for the visit. If an unscheduled visit is conducted due to safety or efficacy reasons, a C-SSRS assessment will be performed with the subject during the visit. If an unscheduled visit is conducted for reasons other than safety or efficacy concerns (eg, replacement of lost medication, repeated collection of a laboratory specimen due to collection or analysis issues), a C-SSRS will not be required at these visits.
- ^b Entry Visit (Visit 1) will be done on the same day as the last visit of parent study. Data from parent study will be used (identified by *) and corresponding assessments will not be repeated.
- ^c The Taper Period is only valid for subjects discontinuing the study or completing without continuation of the PSL treatment. This period will last for 3 weeks plus a 1-week drug-free period.
- ^d Questionnaires to be completed by all subjects prior to any other study procedures at the visit, when possible.
- ^e Assessment is only valid for subjects discontinuing PSL treatment.
- ^f Vital signs measured in supine position after 5 minutes of rest include pulse rate, respiratory rate, systolic BP, and diastolic BP.
- ^g Full physical examination will include assessment of cardiac and respiratory function via auscultation and review of the following body systems: general appearance; ear, nose, and throat; eyes; hair and skin; respiratory; cardiovascular; gastrointestinal; musculoskeletal; hepatic; neurological; and mental status. Brief physical examinations will include a review of the following body systems: general appearance (including mental status); skin; respiratory; cardiovascular; gastrointestinal; and hepatic.
- ^h Brief neurological examination will include a general assessment and evaluation of reflexes, muscle strength and coordination and cerebellar function. Full neurological examination will include in addition, evaluation of cranial nerves, motor system (general muscle strength and tone), and sensations in upper/lower extremities.
- ⁱ Personal outcome assessments will be completed at Visit 6 (Month 6) and Visit 11 (Month 21) (for subjects who agree to participate).
- ^j An ECG at the SFU will be performed only if abnormal at the EOS or EDV Visit. All ECG recordings will be performed with the subject resting in supine position for at least 5 minutes.
- ^k Only subjects who do not require tapering of PSL at M24 will have an echocardiogram at M24. All other subjects will have an echocardiogram at the SFU Visit and at 6 months after the last dose of PSL. A repeat echocardiogram will be performed for subjects with a new finding, Grade 2 severity (moderate), or Grade 3 severity (severe) (see [Section 6.3](#)).
- ^l Results of a serum pregnancy test performed during parent study will be used at Visit 1 together with a urine test performed at Visit 1. Urine pregnancy tests will be used at all other visits for female subjects of childbearing potential.
- ^m Seizure counts are collected on the subject's daily record card on a daily basis.
- ⁿ Assessment includes AED history.
- ^o Medication should be presented at each visit for check on compliance.
- ^p PSL will be dispensed at the EOS Visit only to subjects who will be tapered off PSL.
- ^q The study termination assessment at the EOS visit is for subjects who will transfer into either a Managed Access Program or another PSL study.
- ^r The study termination assessment at the SFU Visit is for subjects who withdraw early or who complete the study, but will not be transferred to either a Managed Access Program or another PSL study.

5.3 Rationale for study design and selection of dose

EP0093 will assess the long-term safety, tolerability, and efficacy of PSL as an adjunctive treatment for focal-onset seizures in adult subjects with drug-resistant epilepsy.

This OLE study will provide subjects, who participated in previous PSL studies, the opportunity to have continued access to PSL.

The individual starting dose of each subject will be the one recommended at the end of the parent study.

This entry dose level was selected considering benefit-risk and is based on clinical pharmacology and positron emission tomography data in healthy human subjects suggesting that it will provide full occupancy at the SV2A binding site while maintaining some minimal binding to the GABA-A binding site. For subjects previously on placebo in the parent study, a full SV2A occupancy is desirable to obtain a meaningful anticonvulsive effect while the minimal benzodiazepine binding more likely will make a better tolerance to GABA-related central nervous system toxicity. On the other hand, participants exposed to a high maintenance dose of PSL in the parent study (800mg/day), a target transition dose of 400mg/day will likely maintain the full SV2A-related effect while not entirely eliminating GABA-binding related effects. Once subjects enter EP0093, further individual dose adjustments are allowed between 100mg/day up to a maximum of 800mg/day to the extent possible with combination of tablet strengths available (ie, 25mg, 100mg, and 200mg).

6 SELECTION AND WITHDRAWAL OF SUBJECTS

6.1 Inclusion criteria

To be eligible to participate in this study, all of the following criteria must be met:

General

1. An Institutional Review Board (IRB)/Independent Ethics Committee (IEC) approved written ICF is signed and dated by the subject or by the parent(s) or legal representative (where legally permitted). The ICF, or a specific Assent form, where required, will be signed and dated by minors, according to country-specific regulations.
2. Subject/legal representative/caregiver (where legally permitted) is considered reliable and capable of adhering to the protocol (eg, able to understand and complete diaries), visit schedule, or medication intake according to the judgment of the Investigator.
3. Subject is an adult (18 years of age or more).

Epilepsy

4. Subject with epilepsy who has completed 1 of the previous PSL studies which allow access to the present study.

Birth control

5. Female subjects of child bearing potential must have a serum negative pregnancy test at the Entry Visit, which is confirmed to be negative by urine testing prior to further dispensing at each study visit thereafter. Subjects will be withdrawn from the study as soon as pregnancy is known.

Female subjects will use an efficient form of contraception for the duration of the study and for a period of 3 months after their final dose of PSL. Hormonal contraception may be susceptible to an interaction with PSL, which may reduce the efficacy of the contraception method. The potential for reduced efficacy of any hormonal contraception method requires that a barrier method (preferably a condom) also be used.

Birth control methods considered as efficient forms of contraception:

- Combined (estrogen- and progesterone-containing) hormonal contraception (oral, implant, injectable) associated with inhibition of ovulation (which must be stable for at least 1 full month prior to the Entry Visit [Visit 1], and should remain stable during the study) in combination with a barrier method (preferably a condom).
- Progesterone-only hormonal contraceptives (oral, implant, injectable) associated with inhibition of ovulation (which must be stable for at least 1 full month prior to Entry Visit [Visit 1], and should remain stable during the study) in combination with a barrier method (preferably a condom).
- Progesterone-releasing intrauterine systems or the TCU 380A intrauterine device in combination with a barrier method (preferably a condom).
- Progestogen-only oral hormonal contraception, where inhibition of ovulation is not the primary mode of action, in combination with a barrier method (preferably a condom).
- Male or female condom with spermicide (ie, double-barrier).
- Cap, diaphragm or sponge with spermicide (ie, double-barrier).
- Bilateral tubal ligation.
- Vasectomized partner (provided sole partner, and partner has medical proof of surgical success).
- True heterosexual sexual abstinence is an acceptable form of contraception when this is in line with the preferred and usual lifestyle of the person. Periodic abstinence (eg, calendar, ovulation, symptothermal, post-ovulation methods), declaration of abstinence for the duration of the study, and withdrawal are not acceptable methods of contraception.
- Women not agreeing to use birth control must be of non-childbearing potential, defined as being postmenopausal (for at least 2 years before the Entry Visit), verified by serum follicle stimulating hormone level >40mIU/mL at the Entry Visit, or permanently sterilized (eg, bilateral tubal occlusion, hysterectomy, bilateral salpingectomy), or congenitally sterile.

Both male and female subjects must use the above-mentioned contraception during the study.

- To ensure a proper birth control, females who use hormonal contraception should use an efficient barrier contraceptive in the 3 months after their final intake of PSL.

6.2 Exclusion criteria

Subjects are not permitted to enroll in the study if any of the following criteria is met:

General

1. Subject has any severe medical, neurological, or psychiatric condition, or laboratory value which may have an impact on the safety of the subject.
2. [REDACTED] as indicated by a positive response (“Yes”) to either Question 4 or Question 5 of the “Since Last Visit” version of the Columbia-Suicide Severity Rating Scale (C-SSRS). The subject should be referred immediately to a mental healthcare professional and must be withdrawn from the study.

Laboratory parameters

3. Subject has $>2x$ upper limit of normal (ULN) of any of the following: alanine aminotransferase (ALT), aspartate aminotransferase (AST), alkaline phosphatase (ALP), or $>ULN$ total bilirubin ($\geq 1.5xULN$ total bilirubin if known Gilbert’s syndrome) at the Entry Visit. If the subject has elevations only in total bilirubin that are $>ULN$ and $<1.5xULN$, fractionated bilirubin must be used to identify possible undiagnosed Gilbert’s syndrome (ie, direct bilirubin $<35\%$).

For enrolled subjects with a Baseline result $>ULN$ for ALT, AST, ALP, or total bilirubin, a Baseline diagnosis and/or the cause of any clinically-significant elevation must be understood and recorded.

If subject has $>ULN$ for ALT, AST, or ALP that does not meet the exclusion limit at the Entry Visit (ie, the value is $>ULN$ but $\leq 2xULN$ at the Entry Visit of EP0093), the tests must be repeated, if possible, prior to dosing to ensure there is no further ongoing clinically-significant increase. In case of a clinically-significant increase, inclusion of the subject must be discussed with the Medical Monitor.

Medical conditions

4. Subject has a clinically-significant abnormality on ECG that, in the opinion of the Investigator, increases the risks associated with participating in the study. In addition, any subject with any of the following findings will be excluded:
 - QT interval corrected for heart rate using Bazett’s formula (QTcB) or QT interval corrected for heart rate using Fridericia’s formula (QTcF) $>450ms$.
 - Bundle branch blocks and other conduction abnormalities that are clinically significant according to the Investigator and/or with a PR interval $\geq 220ms$, irregular rhythms other than sinus arrhythmia or occasional, rare supraventricular or rare ventricular ectopic beats in the judgment of the Investigator, or T-wave configurations are not of sufficient quality for assessing QT interval duration.
 - Subject has a history of unexplained syncope or a family history of sudden death due to long QT syndrome.

5. Subject has an abnormality on echocardiogram at last echocardiogram assessment, or foreseen in parent study as assessed by central reader that is accompanied by clinical symptoms (eg, shortness of breath, palpitations, and murmur) or a Grade 2* (or higher)/moderate severity abnormality, or a history of rheumatic heart disease, or other known valvular abnormalities (*according to the ASE Guidelines, 2017; Zoghbi et al 2017).

Pregnancy

6. Female subject who plans to be pregnant or is breastfeeding.

6.3 Withdrawal criteria

Subjects are free to withdraw from the study at any time, without prejudice to their continued care.

Subjects should be withdrawn from the study if any of the following events occur:

1. Subject withdraws his/her consent.
2. The Sponsor or a regulatory agency requests withdrawal of the subject.
3. Subject is noncompliant with the study procedures or medications in the opinion of the Investigator.
4. Subject and/or Investigator do(es) not think that PSL is effective (ie, lack or loss of efficacy).
5. Subject cannot tolerate the minimum PSL dose of 50mg bid (100mg/day).
6. Subject takes prohibited concomitant medications, prescribed or over-the-counter as defined in this protocol.
7. A prolongation or worsening of overall seizure duration, frequency, type, or pattern considered by the Investigator as serious enough to warrant discontinuation from the study.
8. Subjects with an echocardiogram showing a Grade 2 finding (moderate regurgitation/stenosis) if accompanied with moderate to severe signs/symptoms or a Grade 3 finding (severe regurgitation/stenosis) will be discontinued from the study regardless of accompanying clinical symptoms, and should begin discontinuation of PSL. Additionally, a jump of 2 grades from Grade 0 to Grade 2 (moderate regurgitation/stenosis) accompanied with moderate to severe symptoms or from Grade 1 to Grade 3 (severe regurgitation/stenosis) will result in subject discontinuation (see [Section 6.3.2](#)).
9. Changes in the ECG that are regarded as clinically significant and/or that worsens over time.
 - An ECG shows an absolute value for QTcB or QTcF ≥ 500 ms or ≥ 60 ms above Baseline.
 - Subject develops second- or third-degree atrioventricular block or another clinically-relevant change in ECG as determined by the Investigator.
10. [REDACTED] as indicated by a positive response (“Yes”) to Question 4 of the “Since Last Visit” version of the C-SSRS. The subject should be referred immediately to a mental healthcare professional and may be withdrawn from the study based upon the Investigator’s judgment of the benefit/risk ratio of continuing the subject in the study on PSL.

- [REDACTED] as indicated by a positive response (“Yes”) to Question 5 of the “Since Last Visit” version of the C-SSRS. The subject should be referred immediately to a mental healthcare professional and must be withdrawn from the study.
11. Subject develops an illness that would interfere with his/her continued participation.
 12. For subject developing psychiatric/mood/behavioral signs or disturbances (see examples in list below) that are clinically concerning or that worsen over time, the PSL dose should be gradually reduced and, if symptoms persist, withdrawal from the study should be considered. The subject should be referred to a mental health professional, and continuation of PSL should only be allowed with the approval and under close oversight of the mental health specialist, and upon confirmation of the positive benefit/risk by the Investigator.
 - Auditory or visual hallucinations
 - Delusions/paranoia/grandeur
 - Disorganized thought process
 - Agitation/aggression/apathy
 - Dysphoria/depression/mood lability/euphoria
 - Disinhibition
 - Cognitive changes/memory impairment/delirium
 - Aberrant motor behavior
 13. Subject is suspected of having a serious multiorgan hypersensitivity reaction. Serious suspected multiorgan hypersensitivity cases may be identified and reported to the Sponsor by the Investigator using the following algorithm:
 - An AE or laboratory value (as defined below) suggestive of internal organ involvement including but not limited to hepatitis, nephritis, pneumonitis, carditis, colitis, encephalitis, pancreatitis, myositis, arthritis, or hematologic system involvement combined with at least one of the following: fever, rash, lymphadenopathy, or eosinophilia.
 - Treatment-emergent abnormal laboratory value criteria suggestive of internal organ involvement or eosinophilia:
 - Eosinophils percentage $\geq 10\%$
 - Eosinophils absolute $\geq 0.5\text{G/L}$
 - Neutrophils absolute $< 1.5\text{G/L}$
 - Platelets absolute $\leq 100\text{G/L}$
 14. There is confirmation of a pregnancy during the study, as evidenced by a positive pregnancy test.

Investigators should attempt to obtain information on subjects in the case of withdrawal or discontinuation. For subjects considered as lost to follow up, the Investigator should make an effort (at least 1 phone call and 1 written message to the subject), and document his/her effort

(date and summary of the phone call and copy of the written message in the source documents), to complete the final evaluation. All results of these evaluations and observations, together with a narrative description of the reason(s) for removing the subject, must be recorded in the source documents. The eCRF must document the primary reason for withdrawal or discontinuation.

Investigators should contact the Medical Monitor, whenever possible, to discuss the withdrawal of a subject in advance.

6.3.1 Potential drug-induced liver injury PSL discontinuation criteria

Subjects with potential drug-induced liver injury (PDILI) must be assessed to determine if PSL must be discontinued. In addition, all concomitant medications and herbal supplements that are not medically necessary should also be discontinued.

The PDILI criteria below require immediate and permanent discontinuation of PSL:

- Subjects with either of the following:
 - ALT or AST $\geq 5xULN$
 - ALT or AST $\geq 3xULN$ and coexisting total bilirubin $\geq 2xULN$

The PDILI criterion below requires immediate discontinuation of PSL:

- Subjects with ALT or AST $\geq 3xULN$ who exhibit temporally associated symptoms of hepatitis or hypersensitivity. Hepatitis symptoms include fatigue, nausea, vomiting, right upper quadrant pain or tenderness. Hypersensitivity symptoms include fever (without clear alternative cause), rash, or eosinophilia (ie, $>5\%$).

The PDILI criterion below allows for subjects to continue on PSL at the discretion of the Investigator.

- Subjects with ALT or AST $\geq 3xULN$ (and $\geq 2x$ Baseline) and $<5xULN$, total bilirubin $<2xULN$, and no eosinophilia (ie, $\leq 5\%$), with no fever, rash, or symptoms of hepatitis (eg, fatigue, nausea, vomiting, right upper quadrant pain or tenderness).

Evaluation of PDILI must be initiated immediately. It consists of the diagnostic testing and continued monitoring (specific tests dependent on laboratory results and corresponding symptoms) and consultation with a local hepatologist. The local hepatologist is the expert usually consulted by the treating physician for assessment and management of potential hepatic disease. This would usually be a hepatologist, but may be a gastroenterologist. Additional investigation and monitoring may be required and adapted based on the diagnosis after the cause of the liver injury/abnormality is confirmed.

Evaluation of PDILI must be initiated as described in [Section 9.2.1](#). If subjects are unable to comply with the applicable monitoring schedule, PSL must be discontinued immediately. Investigators should attempt to obtain information on subjects in the case of PSL discontinuation to complete the final evaluation. Subjects with PDILI should not be withdrawn from the study until investigation and monitoring are complete. All results of these evaluations and observations, as well as the reason(s) for PSL discontinuation and subject withdrawal (if applicable), must be recorded in the source documents. The eCRF must document the primary reason for PSL discontinuation.

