9.2.1 Evaluation of PDILI

The PDILI PSL discontinuation criteria for this study are provided in [Section 6.3.1](#), with the accompanying required follow-up investigation and monitoring detailed below. All PDILI events must be reported as an AE and reported to the study site and Sponsor within 24 hours of learning of their occurrence. Any PDILI event that meets the criterion for potential Hy’s Law must be reported as an AE of special interest (see [Section 9.1.1.3](#)), and, if applicable, also reported as an SAE (see [Section 9.1.1.2](#)).

Evaluation of PDILI consists of the diagnostic testing and continued monitoring included in [Table 9-3](#) (specific tests dependent on laboratory results and corresponding symptoms) and consultation with a local hepatologist (if applicable; discussed in [Section 9.2.1.1](#)). The local hepatologist is the expert usually consulted by the treating physician for assessment and management of potential hepatic disease. This would usually be a hepatologist, but may be a gastroenterologist. Additional investigation and monitoring may be required and adapted based on the diagnosis after the cause of the liver injury/abnormality is confirmed (details in [Section 9.2.1.4](#)).

The results of all monitoring, including laboratory testing and other testing, should be made available to the study site and Sponsor.

All initial tests resulting in abnormal hepatic laboratory values need to be repeated, but appropriate medical action must not be delayed waiting for the repeat result.

If tests are done locally for more rapid results, a concurrent sample should also be sent to the central laboratory whenever possible. Medical care decisions are to be made initially using the most rapidly available results and a conservative approach must be taken if the results from the 2 laboratory tests are significantly different. Data from the local and central laboratory are to be recorded on the applicable eCRF pages.

When PSL is discontinued, all concomitant medications and herbal supplements that are not medically necessary should also be discontinued. In these cases, the Investigator should also consider dose reduction for medically necessary concomitant medication and consider changing any medically required concomitant medication known to be hepatotoxic to a suitable alternative.

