When PSL is stopped due to PDILI (as described in [Section 6.3.1](#)), PSL must be permanently discontinued unless a subsequent alternative diagnosis fully explains the hepatic findings. If a subsequent alternative diagnosis fully explains the hepatic findings, and the requirements provided in [Section 9.2.1.2.1](#) are met, rechallenge with PSL may be appropriate after discussion with the Sponsor.

Rechallenge with a substance potentially causing drug-induced liver injury is dangerous, may be fatal, and must not occur.

The approach to investigate PDILI is summarized in [Table 9-3](#).

Table 9-3: Required investigations and follow up for PDILI

Laboratory value			Immediate		Follow up	
ALT or AST	Total bilirubin	Symptoms ^a of hepatitis or hypersensitivity	Consultation requirements	Actions	Testing	Evaluation
≥3xULN	≥2xULN ^b	NA	Hepatology consult. ^c	Immediate, permanent PSL discontinuation.	Essential: Must have repeat liver chemistry values and additional testing completed ASAP (see Section 9.2.1.3); recommended to occur at the site with HCP.	Monitoring of liver chemistry values at least twice per week until values normalize, stabilize, or return to within Baseline values. ^d
≥8xULN	NA	Medical Monitor must be notified within 24 hours (eg, by laboratory alert) and subject discussed with Medical Monitor ASAP.	Immediate, temporary or permanent, PSL discontinuation.			
≥3xULN	NA	Yes				
≥3xULN (and ≥2x Baseline) and <5xULN	<2xULN	No	Discussion with Medical Monitor required if the criterion that allows for PSL continuation is met.	Further investigation – immediate PSL discontinuation not required (see Section 9.2.1.2).	Not required unless otherwise medically indicated (at discretion of Investigator).	
≥5xULN (and ≥2x Baseline)	<2xULN	No	Discussion with Medical Monitor required.	Immediate, permanent PSL discontinuation.	Essential: Every attempt must be made to have repeat liver chemistry values and additional testing completed within 48 hours at the site with HCP (see Section 9.2.1.3).	Monitoring of liver chemistry values at least twice per week until values normalize, stabilize, or return to within Baseline value. ^d

ALP=alkaline phosphatase; ALT=alanine aminotransferase; ASAP=as soon as possible; AST=aspartate aminotransferase; HCP=healthcare practitioner; NA=not applicable; PDILI=potential drug-induced liver injury; ULN=upper limit of normal

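### Section 6.3.1 makes any ALT/AST ≥5xULN a permanent PSL stop, but Table 9-3 appears to allow a temporary stop for symptomatic subjects at 5 to <8xULN

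*Protocol*

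**What the plan says.** Protocol Section 6.3.1 sets three tiers.

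- The first opens with "The PDILI criteria below require immediate and permanent discontinuation of PSL". It covers ALT or AST ≥5xULN on its own, or ≥3xULN together with total bilirubin ≥2xULN.
- The second opens with "The PDILI criterion below requires immediate discontinuation of PSL". It covers ALT or AST ≥3xULN with symptoms of hepatitis or hypersensitivity. It does not use the word permanent and has no upper enzyme limit.
- The third lets the investigator continue PSL at ≥3xULN and <5xULN when the subject is at ≥2x Baseline, bilirubin is <2xULN and there are no symptoms.

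Table 9-3 in Section 9.2.1 sets out actions and follow-up by row. The row whose enzyme cell reads "≥5xULN (and ≥2x Baseline" requires bilirubin <2xULN and symptoms No, and its action is a permanent stop. A separate row covers ≥3xULN with symptoms Yes and bilirubin not applicable. It lies in the block that carries the action "Immediate, temporary or permanent, PSL discontinuation".

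Three further statements bear on how the two places fit together. Section 9.2.1 opens with "The PDILI PSL discontinuation criteria for this study are provided in" and names Section 6.3.1. Section 9.2.1.2 refers sites to both Section 6.3.1 and Table 9-3 for the immediate action. Section 9.2.1 also says that, when PSL is stopped for PDILI, "PSL must be permanently discontinued unless a subsequent alternative diagnosis fully explains the hepatic findings".

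**The concern.** Within one enzyme band, adding symptoms appears to loosen the table's instruction. At 6xULN with normal bilirubin, a subject without symptoms is stopped permanently. The same subject with fatigue or nausea, both of which count as hepatitis symptoms, moves to a row that permits a temporary stop. Section 6.3.1 makes no such distinction at ≥5xULN.

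A site that takes the immediate action from the table could record a temporary stop for a subject whom Section 6.3.1 stops permanently. The label could also affect restart. Section 9.2.1.2.1 opens rechallenge to subjects who met certain PDILI criteria without saying which, so a reader might use the temporary or permanent wording to decide who qualifies.

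**Working it through.** No sample size, power or event figure is involved. The check applies both sets of rules to the same subjects.

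**Inputs.** The tiers are from Section 6.3.1 and the rows from Table 9-3. The table's cell borders are not preserved in the text copy read here, so the action for the symptom row is inferred (see below).

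| ALT/AST | Bilirubin | Symptoms | Multiple of Baseline | Section 6.3.1 | Table 9-3 | Result |
|---|---|---|---|---|---|---|
| 4xULN | 1xULN | Yes | any | Immediate, permanence not stated | Symptom row: temporary or permanent | Compatible |
| 6xULN | 1xULN | No | 4 | Permanent | ≥5xULN row: permanent | Agree |
| 6xULN | 1xULN | Yes | any | Permanent | Symptom row only: temporary or permanent | Conflict |
| 6xULN | 1xULN | No | 1.5 | Permanent | No row applies | Gap |
| 6xULN | 3xULN | Yes | any | Permanent | Bilirubin row (permanent) and symptom row | Permanent stop covered |
| 6xULN | 3xULN | No | any | Permanent | Bilirubin row: permanent | Agree |

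The conflict in the third line is the same whether the ≥8xULN row is read as permanent or as temporary or permanent, because a subject at 6xULN does not meet that row.

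**Which action belongs to the symptom row.** The upper block of the table has three rows (bilirubin ≥2xULN, ≥8xULN, symptoms) and two action texts: first permanent, then temporary or permanent. If action cells are merged, the symptom row comes last and takes the second text, wherever the ≥8xULN row falls. Section 6.3.1 supports this, since its symptom tier also leaves out permanence. The alternative is that temporary or permanent belongs to the ≥8xULN row alone. The conflict would then not arise in this form. But the symptom row would have no action text of its own, and the highest enzyme band would be looser than the ≥5xULN row.

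**Whether the Baseline gap can occur.** This depends on which Baseline is meant.

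- If it is the Entry Visit value, exclusion criterion 3 caps ALT and AST at 2xULN. A value of at least 5xULN is then at least 5 / 2 = 2.5 times Baseline, the ≥2x Baseline condition is always met, and the gap is empty.
- If it is the parent-study value, which is the default in SAP Sections 3.3 and 3.3.2, a subject at 5xULN is below 2x Baseline when Baseline exceeds 5 / 2 = 2.5xULN. The line with 6xULN at 1.5 times Baseline corresponds to a Baseline of 6 / 1.5 = 4xULN. The parent study's enzyme limits are not in these documents, so the gap can be neither confirmed nor ruled out.

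**The case against.** The strongest reply is that the protocol already resolves the matter. Section 9.2.1 assigns the stop criteria to Section 6.3.1, and the title of Table 9-3 refers to investigations and follow-up. On that view the table's wording is a range for all symptomatic subjects from 3xULN up, and Section 6.3.1 fixes the answer at ≥5xULN. Section 6.3.1 has the same overlap itself: a symptomatic subject at 6xULN meets both its first and second tiers, and a careful reader takes the stricter. PSL stops at once under either label, the Medical Monitor must be told within 24 hours (Section 9.2.1.1), and restart needs approval from the Study Physician, the DMC and a hepatologist (Section 9.2.1.2.1). The symptomatic block also has the faster work-up: "Must have repeat liver chemistry values and additional testing completed ASAP", against "additional testing completed within 48 hours at the site with HCP" in the asymptomatic ≥5xULN row.

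Most of this stands, and it is why the effect is small. It does not remove the conflict. The table has its own action column, Section 9.2.1.2 sends sites to both places, and neither is said to prevail.

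A reader might infer three stronger points, none of which the documents support.

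- **That subjects at ≥8xULN are also treated too loosely.** This rests on a cell that may be merged or displaced, so it needs checking against the original table.
- **That the conflict covers everyone at ≥5xULN with symptoms.** At bilirubin ≥2xULN a permanent row always applies.
- **That subjects could resume PSL on a lower standard.** Section 9.2.1 treats every PDILI stop as permanent unless another cause is established, and sets the same restart conditions whatever the label.

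**Conclusion.** The point holds as an internal contradiction in a hepatic stopping rule: wrong as written, minor in severity. It concerns symptomatic subjects at 5 to <8xULN with bilirubin <2xULN. Asymptomatic subjects in the same band at <2x Baseline are added only if Baseline is the parent-study value and such Baselines were admitted.

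The main conclusion assumes that the symptom row carries the temporary or permanent action. That is the most natural reading but has not been verified against the original layout. The number of subjects affected cannot be estimated from the documents. No endpoint or analysis changes: SAP Section 9.4 tabulates potential Hy's Law, not temporary against permanent stops.

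**What to change.** Change Table 9-3 only.

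1. Restrict the temporary or permanent action in the symptom row to ALT/AST ≥3xULN and <5xULN with bilirubin <2xULN.
2. State that ALT/AST ≥5xULN means immediate, permanent discontinuation regardless of symptoms or Baseline multiple. Give symptomatic subjects at ≥5xULN their own row, so that they keep the as-soon-as-possible work-up and the 24-hour Medical Monitor notification. Moving them into the existing ≥5xULN row would give them the slower 48-hour work-up.
3. Add a note that Section 6.3.1 governs discontinuation and that the stricter action applies where rows overlap.

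Check the original layout of the ≥8xULN row, and change it only if it does not already say permanent. Leave the rechallenge conditions in Section 9.2.1.2.1 as they are.

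The cost is wording in one table, with no new data, assessments or timelines. Since the SAP records early termination of the study, a short clarification to sites would serve for any subjects still taking or tapering PSL.
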